2.0 STUDY OBJECTIVES

2.1 Primary Objectives

To determine the clinical activity of Avelumab in the management of R/M nasopharyngeal carcinoma.

2.2 Secondary Objectives

- 1. To determine duration of response
- 2. To determine progression-free survival at 6 and 12 months
- 3. To determine overall survival
- 4. To assess safety and tolerability of Avelumab
- 5. To evaluate correlation between molecular markers and disease outcome
- 6. To determine clinical activity using immune-related RECIST.

2.3 Endpoints

Primary Endpoint:

1. Overall response rate (defined as complete or partial response) at 6 months based on RECIST.

Secondary Endpoints:

- 1. Duration of response, defined as time from documentation of tumor response to disease progression
- 2. Progression-free survival, defined as the time start of Avelumab until disease progression or death
- 3. Overall survival, defined as the time from start of Avelumab to death from any cause

- 4. Toxicity (grade 3 or higher), as defined by CTCAE 4.03.
- 5. Exploratory correlatives:
 - Tissue (new biopsy required upon study entry prior to therapy; repeat biopsy at time of progression will be encouraged but optional):
 - PDL1 expression by immunohistochemistry (ABC technique [Vector labs], using rabbit mAb 1:200 [Cell Signaling])
 - Immunophenotyping by flow cytometry:
 - T cell subsets (CD4, CD8, FOXP3)
 - Macrophages (CD68)
 - Cytokeratin 5/6 (by immunohistochemistry)
 - Peripheral blood (comparison of baseline and 12 week post-treatment samples, unless otherwise denoted)
 - TCR and BCR sequencing
 - T cell subsets (CD3, CD4, CD8, CD25, FOXP3)
 - B cells (CD19, CD20)
 - Macrophage I/II and myeloid-derived suppressor cells (MDSC) (CD16, CD68, CD206)
 - Natural killer cell activity (CD56, CD16)
 - EBV DNA plasma levels (will be performed at baseline, every 12 weeks after treatment initiation and at end of treatment)
- 6. Clinical activity of Avelumab as defined by overall response rate will also be measured utilizing immune-related RECIST.

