4.0 TREATMENT PLAN

4.1 Study Design

This is a prospective, multi-center, open-label, single-arm phase II trial to evaluate the efficacy of Avelumab for patients with recurrent/metastatic, EBV-related nasopharyngeal carcinoma. A total of 39 patients will be eligible to enroll. Patients will be enrolled at 7 sites: UC San Diego Moores Cancer Center, Stanford Cancer Institute, UC Los Angeles Jonsson Comprehensive Cancer Center, UC Irvine Chao Cancer Center, University of Southern California Norris Comprehensive Cancer Center, Providence Cancer Center, and Dana-Farber Cancer Institute.

All patients providing informed consent will be screened for eligibility. Baseline assessments will include vital signs, physical exam, ECOG performance status evaluation, blood hematology and chemistries, urinalysis and tumor imaging. Upon study entry, all patients will receive Avelumab 10mg/kg IV on days 1 and 15 of each 28-day cycle. Treatment will be given until disease progression, unacceptable toxicity, investigator decision or patient withdrawal. Dose reductions and/or interruptions may occur per pre-specified criteria for grade 3 or higher toxicity.

History and physical examination, adverse event assessment and routine bloodwork will be performed prior to every cycle. For patients with known hepatic metastases at time of study entry, liver function tests (including ALT, AST, total bilirubin, and alkaline phosphatase) must be performed once weekly for 7 weeks upon treatment initiation. All patients will undergo imaging (CT, MRI, or PET/CT [CT must be diagnostic quality]) within 4 weeks prior to study entry, 12 weeks after treatment initiation (+/- 7 days), and then every 12 weeks thereafter (+/-7 days). Response will be assessed using RECIST. For patients who are clinically stable, a repeat scan will be required 4 weeks (+/- 7 days) after initial radiographic findings of disease progression as a confirmatory assessment.

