4.9 End of Study Treatment and Follow Up

After the last dose of study treatment, each patient will be followed for 28 days for adverse event monitoring (serious adverse events will be collected for 90 days after the end of treatment as described in Section 7.1). Patients removed from treatment for unacceptable adverse events will be followed until resolution or stabilization of the adverse event.

Patients who discontinue for reasons other than progressive disease will have post-treatment follow-up approximately every 3 months for disease status until disease progression, initiation of a non-study cancer treatment, withdrawal of consent or lost to follow-up.

After documented disease progression, each patient will be followed approximately every 3-6 months by review of medical records, telephone, or review of the Social Security Index for overall survival until death, withdrawal of consent, or the end of the study, whichever occurs first.

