6.2.2 Progression-Free Survival

Progression-free survival (PFS) is defined as the duration of time from start of treatment until objective tumor progression or death.

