6.2.3 Time to Progression

Time to progression is defined as the duration of time from start of treatment until objective tumor progression.

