9.4 Secondary Efficacy Analyses

Secondary analysis will present duration of response, progression-free survival, and overall survival. We will estimate median survival times together with their 95% confidence intervals, and report number of events, as well as Kaplan Meier plots with 95% confidence bands.

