2.4.2 Duration of overall response

The duration of overall response is measured from the time measurement criteria are first met for CR/PR (whichever is first recorded) until the first date that recurrent or progressive disease is objectively documented (taking as reference for progressive disease the smallest measurements recorded on study).

The duration of overall complete response is measured from the time measurement criteria are first met for CR until the first date that recurrent disease is objectively documented.

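### Duration of response ends only at progression, so a responder's death without documented progression is a non-event and can lengthen the reported median

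*Combined protocol and SAP*

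**What the plan says.** Section 2.3, secondary endpoint 1: "Duration of response, defined as time from documentation of tumor response to disease progression". Appendix A 2.4.2 likewise measures duration of overall response "until the first date that recurrent or progressive disease is objectively documented". Neither names death.

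Secondary endpoint 2 in the same list does: "Progression-free survival, defined as the time start of Avelumab until disease progression or death". Section 6.2.2 repeats this, with PFS "defined as the duration of time from start of treatment until objective tumor progression or death". A progression-only quantity is also defined, in 6.2.3: "Time to progression is defined as the duration of time from start of treatment until objective tumor progression".

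Section 9.4 treats duration of response, PFS and overall survival together: "We will estimate median survival times together with their 95% confidence intervals, and report number of events, as well as Kaplan Meier plots". It gives no event definition, no censoring date and no competing-risk method for duration of response. Sections 4.9 and 5.4 say when disease follow-up stops, but that is a visit rule and not a censoring rule.

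**The concern.** Kaplan-Meier needs every responder classed as an event or as censored at a date. Under 2.3, a responder who dies without documented progression is not an event, so in practice that patient is censored. Censoring treats the patient as if progression would have come later at the same rate as in those still at risk. The same death is an event for PFS.

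The follow-up plan allows such deaths:

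- Imaging is at 12 weeks "and then every 12 weeks thereafter", so a patient can die between scans.
- Patients who stop treatment without progression have "post-treatment follow-up approximately every 3 months for disease status until disease progression, initiation of a non-study cancer treatment", while survival contact continues until death (5.4).
- Appendix A 2.3.4 says symptomatic deterioration is not an objective response category.

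The three-monthly off-treatment assessments, and the instruction in Appendix A 2.3.4 to try to document progression after treatment stops, make these deaths fewer.

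At stake is how the reported median is read. It would normally be taken as the time responders stayed alive and progression-free. With deaths censored at death it is equal to or longer than that. The number of responders may be small, so one or two deaths can matter.

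**Working it through.** **Number of responders.** The plan gives no expected median, event count or precision for duration of response, so there is no such figure to reproduce. The responder count comes from 9.2 (stop at 3 or fewer of 19; success at 9 or more of 39). Exact binomial calculation reproduces that design:

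- early stopping at p = 15%: P(X ≤ 3 | n = 19) = 0.684 (stated 68.4%)
- type I error 0.097 (limit 10%)
- power at 30%: 0.803 (stated 80%)

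The success boundary is therefore 9 responders. At p = 30%, 39 × 0.30 = 11.7 are expected.

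**Assumption.** Let f be the share of response endings that are deaths without documented progression. The documents give no value, so 5%, 10% and 20% are used. At f = 0 the effect is zero. Section 1.1 gives first-line PFS of 5-6 months against overall survival of 19-21 months. That suggests most deaths follow progression, though the setting is different.

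**Exact calculation, deaths censored at the death date.** Take 9 fully followed responders with ordered endings. Each ending is a death with probability f, independent of order. The median is the first time S ≤ 0.5.

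- All deaths counted: S = 5/9 = 0.556 after the 4th ending and 4/9 = 0.444 after the 5th, so the median is the 5th ending.
- Death at position 1 only: S = 4/8 = 0.5 at the 5th ending, so the median is unchanged.
- Death at position 2 only: S = 8/9 × 6/7 × 5/6 × 4/5 = 0.508 at the 5th ending, so the median moves to the 6th. A single death at position 3, 4 or 5 does the same.
- Deaths at positions 6 to 9 come too late to matter.

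Across all 2^9 = 512 patterns the median is unchanged only when none of positions 2 to 5 is a death. So P(unchanged) = (1 − f)^4 and P(rises) = 1 − (1 − f)^4. It never falls.

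| f | expected such deaths (9f) | P(at least one) = 1 − (1 − f)^9 | P(median rises) | P(unchanged) |
|---|---|---|---|---|
| 5% | 0.45 | 0.370 | 0.19 | 0.81 |
| 10% | 0.90 | 0.613 | 0.34 | 0.66 |
| 20% | 1.80 | 0.866 | 0.59 | 0.41 |

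**Size of the shift.** With constant hazards, the progression-only median is 1/(1 − f) times the progression-or-death median: 1.05, 1.11 and 1.25. For an assumed progression-only median of 9 months, counting deaths gives 9 × (1 − f) = 8.55, 8.1 and 7.2 months.

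**Does the censoring date matter?** Simulation with 9 exponential durations, an assumed 9-month median and a last scan up to 12 weeks before death: the Kaplan-Meier median under death-date censoring differs from that under last-scan censoring in about 3-4%, 6% and 9% of runs at f = 5%, 10% and 20%. Against a progression-or-death duration, last-scan censoring raises the median in about 15%, 29% and 51% of runs and lowers it in under 0.3%.

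**Sensitivity.** A second simulation used 12-week scans (±1 week), a 104-week cutoff, an assumed 39-week progression median and death shares of 10-30%. Counting versus censoring deaths changed the median in 34-74% of trials with 9 responders and 53-93% with 12. Death date versus last scan changed it in 5-10% and 2-11%. The driver is whether death counts, not where it is censored.

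**The case against.** The strongest reply is that the definition is complete and may be deliberate. It has a start and an end, it follows the RECIST text in the appendix, and the protocol names death where it wants death counted. A progression-only time to progression is defined as well. Counting death therefore changes the quantity being estimated. Such deaths may also be rare, the endpoint carries no test or threshold, and PFS and overall survival already count them.

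Most of this stands. There is no contradiction, the true size is unknown, and the consequence is limited. What does not follow is that nothing needs saying. Even if progression-only is intended, 9.4 is silent on how a death enters the Kaplan-Meier estimate, and a plain reader would take the median as time alive and in response.

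Two stronger readings are tempting:

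- A reader might infer that the median hinges on the unstated censoring date. It does not: the two usual choices disagree in under a tenth of runs when scans are current.
- A reader might infer that the shift has no predictable direction. A case can be built. Eight responders progress at times 1 to 8, and a ninth is last scanned at 0.5 and dies at 8.5. The median is 5 with the death counted and 4 if it is censored at 0.5. For this to be common, long gaps would be needed for most deaths, which the 12-weekly and three-monthly assessments do not support. The long gaps arise mainly after new therapy, where it is arguable whether a death should end the response at all.

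**Conclusion.** The point holds as an incomplete specification with a cheap remedy. As written, a responder's death without documented progression is a non-event. If censored at death, it leaves the median unchanged or longer, never shorter. For 9 responders the chance of a longer median is 19%, 34% or 59% at assumed death shares of 5%, 10% or 20%. These figures assume full follow-up and deaths unrelated to the order of endings. The share itself is not in the documents, and at zero the effect vanishes.

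A reader might infer that the trial's conclusion is at risk. The documents do not support that: the primary response test, the sample size and the stopping rule do not use duration of response.

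**What to change.** - **Section 2.3, item 1:** define duration of response as the time from first documented CR or PR to first documented progression or death from any cause, whichever comes first.
- **Appendix A 2.4.2:** note that this trial counts death as an event.
- **Section 9.4:** state that responders alive without progression are censored at their last evaluable tumor assessment.
- **New anti-cancer therapy:** any rule should be the same for duration of response and PFS. Neither has one now, and adding it to one alone would leave the same death treated differently in the two.

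The cost is two clauses and one sentence. Death dates are already collected for PFS and overall survival. The downsides are that the reported median may be shorter and that the definition departs from the literal RECIST wording. Also, a death after missed scans counts at its own date, which can lengthen that patient's duration.

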3.0 PATIENT ELIGIBILITY

3.1 Inclusion Criteria

Patients must meet all of the inclusion criteria to participate in this study.

- 1. Patient has the ability to understand and the willingness to sign a written informed consent.
- 2. Patient has histologically/cytologically confirmed, non-keratinizing/undifferentiated, EBVrelated nasopharyngeal carcinoma, not amenable to curative intent therapy. EBV testing may be completed per institutional standards.
- 3. Patient must have at least one measurable site of disease as defined by RECIST v1.1, determined by investigator review
- 4. Patient has received at least one prior line of systemic therapy in the recurrent/metastatic setting.
- 5. Patient is willing to undergo a fresh tumor biopsy (core or excisional) for correlative analyses (ie. PD-L1 expression). The study chair may grant exceptions to the mandatory biopsy should the treating physician deem that a biopsy is not feasible or unsafe for the patient, and archival tissue is available and provided for study purposes. A conversation with the study chair is required to obtain an exception.
- 6. Age \geq 18 years.
- 7. Eastern Cooperative Oncology Group (ECOG) Performance status of 0-2.

Grade	Descriptions				
0	Normal activity. Fully active, able to carry on all pre-disease performance without restriction.				
1	Symptoms, but ambulatory. Restricted in physically strenuous activity, but ambulatory and able to carry out work of a light or sedentary nature (e.g., light housework, office work).				
2	In bed < 50% of the time. Ambulatory and capable of all self-care, but unable to carry out any work activities. Up and about more than 50% of waking hours.				
3	In bed > 50% of the time. Capable of only limited self-care, confined to bed or chair more than 50% of waking hours.				
4	100% bedridden. Completely disabled. Cannot carry on any self-care. Totally confined to bed or chair.				
5	Dead.				

- 8. Patient has adequate organ and marrow function as defined below:
 - Absolute Neutrophil Count
 - Platelet count
 - Hemoglobin
 - Total bilirubin
 - AST/SGOT and ALT/SPGT
 - Albumin
 - Serum creatinine

 \geq 2.0 g/dL \leq 1.5 x institution's ULN, or creatinine

 \leq 1.5 x institution's upper limit of normal

≤ 2.5 X institutional upper limit of normal

clearance \geq 60 ml/min

 $\ge 1.0 \times 10^{9}/L$ $\ge 75 \times 10^{9}/L$

≥ 8.0 g/dL

- 9. Female patient of childbearing potential has a negative serum or urine pregnancy within 72 hours prior to receiving the first dose of study medication.
- 10. Female patient of childbearing potential agrees to use 2 methods of birth control or be surgically sterile, or abstain from heterosexual activity for the course of the study through 120 days after the last dose of study medication (Reference Section 4.6.2).

Note: Females of childbearing potential are those who have not been surgically sterilized or have not been free from menses for > 1 year.

11. Male patient with a partner of childbearing potential agrees to use an adequate method of contraception starting with the first dose of study therapy through 120 days after the last dose of study therapy.

3.2 Exclusion Criteria

Patients meeting any of the exclusion criteria at baseline will be excluded from study participation.

- 1. Patient is currently receiving or has received another investigational agent within 4 weeks prior to Day 1 of study.
- 2. Patient has received chemotherapy or radiotherapy within 4 weeks prior to Day 1 of study. Prior palliative radiotherapy to metastatic lesion(s) is permitted, provided there is at least one measurable lesion that has not been radiated.
- 3. Patient has received prior immunotherapy with inhibitors of PD-1/PD-L1 axis.

- 4. Patient has had major surgery or insufficient recovery from surgical-related trauma or wound healing within 14 days of Study Day 1.
- 5. Patient has had a prior Grade ≥ 3 immune-related adverse event (irAE) while receiving any previous immunotherapy agent, or any unresolved irAE > Grade 1.
- 6. Patient has a known additional malignancy that is progressing or requires active treatment. Exceptions include basal cell carcinoma of the skin or squamous cell carcinoma of the skin that has undergone potentially curative therapy or *in situ* cervical cancer.
- 7. Patient has known active central nervous system (CNS) metastases and/or carcinomatous meningitis.

Note: Patients with previously treated brain metastases may participate provided they are stable (without evidence of progression by imaging for at least four weeks prior to the first dose of trial treatment and any neurologic symptoms have returned to baseline), have no evidence of new or enlarging brain metastases, and are not using steroids for at least 7 days prior to trial treatment. This exception does not include carcinomatous meningitis which is excluded regardless of clinical stability.

 Patient has an active autoimmune disease that has required systemic treatment in the past 2 years (i.e. with use of disease modifying agents, corticosteroids or immunosuppressive drugs).

Notes:

- Patients with vitiligo, Grave's disease, or psoriasis not requiring systemic treatment within the past 2 years are not excluded.
- Replacement therapy (e.g., thyroxine, insulin, or physiologic corticosteroid replacement therapy for adrenal or pituitary insufficiency, etc.) is not considered a form of systemic treatment.
- Patient has a diagnosis of immunodeficiency, or is receiving systemic steroid therapy (>10mg prednisone daily, or steroid equivalent) or any other form of immunosuppressive therapy within 7 days prior to the first dose of avelumab.
- 10. Patient has a known history of active TB (Baccillus Tuberculosis).
- 11. Patient has a known history of, or any evidence of active, non-infectious pneumonitis.
- 12. Patient has a known history of chronic interstitial lung disease.
- 13. Patient has an active infection requiring systemic therapy.
- 14. Patient has a history or current evidence of any condition, therapy, or laboratory abnormality that might confound the results of the trial, interfere with the subject's participation for the full duration of the trial, or is not in the best interest of the subject to participate, in the opinion of the treating investigator.
- 15. Patient has a known psychiatric or substance abuse disorder that would interfere with cooperation with the requirements of the trial.

- 16. Patient is pregnant or breastfeeding, or expecting to conceive or father children within the projected duration of the trial.
- 17. Patient has known active Hepatitis B infection (defined as presence of HepB sAg and/ or Hep B DNA), active hepatitis C infection (defined as presence of Hep C RNA) and/or known Human Immunodeficiency Virus (HIV).
 - Patients with HIV who have a normal CD4 count (≥ 200) and an undetectable viral load are not excluded.
- 18. Patient has received a live vaccine within 30 days of study Day 1. Note: Seasonal influenza vaccines for injection are generally inactivated flu vaccines and are allowed; however intranasal influenza vaccines (e.g., Flu-Mist®) are live attenuated vaccines, and are not allowed.

4.0 TREATMENT PLAN

4.1 Study Design

This is a prospective, multi-center, open-label, single-arm phase II trial to evaluate the efficacy of Avelumab for patients with recurrent/metastatic, EBV-related nasopharyngeal carcinoma. A total of 39 patients will be eligible to enroll. Patients will be enrolled at 7 sites: UC San Diego Moores Cancer Center, Stanford Cancer Institute, UC Los Angeles Jonsson Comprehensive Cancer Center, UC Irvine Chao Cancer Center, University of Southern California Norris Comprehensive Cancer Center, Providence Cancer Center, and Dana-Farber Cancer Institute.

All patients providing informed consent will be screened for eligibility. Baseline assessments will include vital signs, physical exam, ECOG performance status evaluation, blood hematology and chemistries, urinalysis and tumor imaging. Upon study entry, all patients will receive Avelumab 10mg/kg IV on days 1 and 15 of each 28-day cycle. Treatment will be given until disease progression, unacceptable toxicity, investigator decision or patient withdrawal. Dose reductions and/or interruptions may occur per pre-specified criteria for grade 3 or higher toxicity.

History and physical examination, adverse event assessment and routine bloodwork will be performed prior to every cycle. For patients with known hepatic metastases at time of study entry, liver function tests (including ALT, AST, total bilirubin, and alkaline phosphatase) must be performed once weekly for 7 weeks upon treatment initiation. All patients will undergo imaging (CT, MRI, or PET/CT [CT must be diagnostic quality]) within 4 weeks prior to study entry, 12 weeks after treatment initiation (+/- 7 days), and then every 12 weeks thereafter (+/-7 days). Response will be assessed using RECIST. For patients who are clinically stable, a repeat scan will be required 4 weeks (+/- 7 days) after initial radiographic findings of disease progression as a confirmatory assessment.

A newly obtained tumor specimen will be obtained prior to study entry (unless it is not feasible or deemed unsafe for the patient, archival tissue is available, and study chair has granted an exception) for the purposes of measuring PD-L1 expression, T cell subsets etc. Patients will also provide blood samples at baseline and 12 weeks after treatment initiation for correlative studies, including PBMCs, T and B-cell subsets, frequency and clonality. Peripheral blood will be collected at baseline, and then every 12 weeks after treatment initiation as well as at end of treatment for serial measurement of EBV plasma DNA levels. Additionally, at time of disease progression, patients will be encouraged but not mandated to undergo a second biopsy for study purposes to permit further correlative studies.

An end of treatment visit for clinical evaluations and safety assessments will be performed approximately 28 days (\pm 7 days) after the last dose of study drug. Patients discontinuing study treatment will be followed every 3 months for disease and survival outcomes.

